## GI disorders

### Constipation (for erdafitinib only)

Grade 1	Maintain dose level of erdafitinib, but initiate anti-constipation treatment.
Grade 2	Omit dose of erdafitinib until resolved to CTCAE Grade ≤ 1, then maintain dose level of erdafitinib.

Grade 3	Omit dose of erdafitinib until resolved to CTCAE Grade ≤ 1, then reduce dose of erdafitinib by 1 dose level.
Grade 4	Discontinue erdafitinib.
Diarrhea (for palbociclib only)	
Grade 1	Maintain dose level of palbociclib, initiate anti-diarrhea treatment per standard practice.
Grade 2	Initiate anti-diarrhea treatment per standard practice.  Omit dose of palbociclib until resolved to CTCAE Grade ≤ 1, then maintain dose level of palbociclib.  For 2nd occurrence of diarrhea CTCAE Grade 2, omit dose of palbociclib until resolved to CTCAE Grade ≤ 1, then reduce palbociclib by 1 dose level.
Grade 3	Initiate anti-diarrhea treatment per standard practice.  Omit dose of palbociclib until resolved to CTCAE Grade ≤ 1, then reduce dose of palbociclib by 1 dose level.  For 2nd occurrence of diarrhea CTCAE Grade 3, discontinue palbociclib.
Grade 4	Initiate anti-diarrhea treatment per standard practice.  Discontinue palbociclib.
Note: Antidiarrheal medication per standard practice is recommended at the first sign of abdominal cramping, loose stools or overt diarrhea.	
Mucositis	
Grade 1	Continue palbociclib and erdafitinib at same doses.  Topical steroid moderate strength and lidocaine 2-5% jelly or solution QID.
Grade 2	Continue palbociclib and erdafitinib at current dose.  Dexamethasone solution (3.3 mg/5 mL) swish and spit QID and lidocaine 2-5% jelly or solution QID.  Consider study drug holding if no improvement in 1 week.  When resolves to ≤Grade 1 or baseline, restart at same or 1 dose level below in consultation with the medical monitor.
Grade 3	Hold palbociclib and erdafitinib (for up to 28 days), with weekly reassessments of clinical condition.  Dexamethasone solution (3.3 mg/5 mL) swish and spit QID and lidocaine 2-5% jelly or solution QID  When resolves to ≤Grade 1 or baseline, restart at 1 dose level below in consultation with the medical monitor.
Grade 4	Discontinue palbociclib and erdafitinib; evaluation and therapy as clinically indicated.
Skin and subcutaneous disorders (for erdafitinib only)	
Skin toxicity	
Grade 1	Maintain dose level of erdafitinib.  Use fragrance free moisturizing cream or ointment BID over entire body.  Use ammonium lactate 12% cream or salicylic acid 6% cream BID over dry/scaly/hyperkeratotic areas such as palms and soles.

Grade 2	Maintain dose level of erdafitinib.  Use fragrance free moisturizing cream or ointment BID over entire body.  Use ammonium lactate 12% cream or salicylic acid 6% cream BID over dry/scaly/hyperkeratotic areas such as palms and soles.  Use zinc oxide 13-40% at night for areas with fissures.
Grade 3	Omit erdafitinib doses for up to 28 days, with weekly assessments of clinical condition.  Use topical steroid ointment or cream (Clobetasol 0.05%, Betamethasone 0.05%, Fluocinonide 0.05%) BID and zinc oxide 13-40% at night for areas with fissures.  Once resolved to grade ≤ 1 then:  - If resolved in ≤ 14 days, ↓ 1 dose level of erdafitinib. - If resolved in > 14 days, discontinue patient from erdafitinib.
Grade 4	Discontinue erdafitinib; therapy as clinically indicated.
Nail toxicity	
Grade 1	Maintain dose level of erdafitinib.  Over the counter nail strengthener OR poly-urea urethane nail lacquer (Nuvail) OR diethylene glycol monoethylether nail lacquer daily (Genadur).
Grade 2	Maintain dose level of erdafitinib.  For signs of infection (periungal edema/erythema/ tenderness and/or discharge), start the following:  - treatment with oral antibiotic for 2 weeks (cefadroxil 500 mg BID, ciprofloxacin 500 mg BID, or sulfamethoxazole/ trimethoprim (Bactrim®) DS BID) AND  - topical antifungal lacquer daily for 6+ weeks (ciclopirox olamine 8% OR efinaconazole 10% OR amorolfine 5% weekly OR bifonazole/urea ointment daily)  Consider study drug holding if no improvement in 1 to 2 weeks.  When resolved to ≤ Grade 1 or baseline, restart at same or 1 dose level below in consultation with the medical monitor.
Grade 3	Hold erdafitinib (for up to 28 days), with weekly reassessments of clinical condition.  Silver nitrate application weekly AND topical antibiotics (Mupirocin 2%, gentamycin, bacitracin zinc/polymixin B) AND vinegar soaks (soaking fingers or toes in a solution of white vinegar in water 1:1 for 15 minutes every day).  For signs of infection (periungal edema/erythema/ tenderness and/or discharge), start the following: treatment with oral antibiotic for 2 weeks (cefadroxil 500 mg BID, ciprofloxacin 500 mg BID, or sulfamethoxazole/trimethoprim (Bactrim®) DS BID).  For cases of severe/refractory infection consider intravenous antibiotics.  Consider dermatological and/or surgical evaluation if necessary.  When resolved to ≤Grade 1 or baseline, restart at 1 dose level below in consultation with the medical monitor.

Grade 4	Discontinue erdafitinib, evaluation and therapy as clinically indicated.
General disorders (for erdafitinib only)	
Fatigue/ asthenia	
Grade 1 / 2	Maintain dose level of erdafitinib.
Grade 3	Omit dose of erdafitinib until resolved to CTCAE Grade $\leq 1$ , then - If resolved in $\leq 7$ days, maintain dose level of Erdafitinib. - If resolved in $> 7$ days, discontinue patient from Erdafitinib.
Other AEs	
Grade 1 / 2	Maintain dose level of palbociclib and erdafitinib.
Grade 3	Omit dose of palbociclib and erdafitinib until resolved to CTCAE Grade $\leq 1$ , then $\downarrow$ dose level of palbociclib and erdafitinib.
Grade 4	Discontinue palbociclib and erdafitinib.

 
• All dose modifications should be based on the worst preceding toxicity. Once a dose has been reduced it will not be increased at a later time even if there is no toxicity. Patients who require dose reductions of palbociclib and erdafitinib past the lowest dose level will be discontinued from study drugs treatment.
 
• If a patient requires a dose delay of <math>> 28</math> consecutive days from the intended day of the next scheduled dose of palbociclib and erdafitinib, due to study related interventions, then the patient must be discontinued from the study treatment. Patients that require a dose delay of <math>> 28</math> days due to a cause unrelated to study participation will have the opportunity to continue study if deemed eligible to do so by the Protocol Chair of the study. Patients who discontinue from the study for a study-related AE or an abnormal laboratory value must be followed at least once a week for 4 weeks and subsequently at 4-week intervals, until resolution or stabilization of the event, whichever comes first, except specifically mentioned.
 
	

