## 7.5 Definition of Maximum Tolerated Dose (MTD)

The MTD will be defined as the highest dose at which 20% of the patients experienced a DLT. The first cohort of patients (3 patients) will be started at dose level 1, and each patient will be observed for 4 weeks on the specified dose. No new cohort of patients will be treated until the previous cohort has been fully evaluated for toxicity and a dose escalation decision has been made. Routine updates regarding patient and study status will be conducted.

Once the MTD is reached, the safety data will be analyzed and the expansion component of the study will be completed to assess tolerability and efficacy. Patients in the phase II portion of the study will initiate study treatment at the MTD defined in the escalation component of the trial. Note that dose reduction within patients (individually) is allowed after the 4 week DLT observation period in the escalation and in the expansion components of the study (see Dose Modification guidelines, Section 8). Intrapatient dose escalation will not be allowed. Dose reduction will be required for a given patient in case of:

- Grade 3 or 4 toxicities
- Grade  $\geq 2$  hyperphosphatemia lasting more than 21 days despite medical treatment, or
- Grade  $\geq 2$  ocular toxicity lasting more than 28 days despite medical treatment, or
- Grade  $\geq 2$  elevation of creatinine, bilirubin, AST, or ALT lasting more than 14 days despite medical treatment, or
- Grade  $\geq 2$  skin or nail toxicity for more than 28 days in a row despite optimal medical treatment, or

- Grade  $\geq$  2 GI toxicity lasting more than 14 days despite medical treatment.

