## **8. EXPECTED TOXICITIES AND DOSING DELAYS/DOSE MODIFICATIONS**

### **8.1 Erdafitinib**

#### **8.1.1 Most common anticipated toxicities (refer to IB for further details)**

- Hyperphosphatemia
- Decrease in appetite
- Dry mouth
- Nail and skin toxicities
- Palmar-plantar erythrodysesthesia
- Mucositis (mouth sores)
- Dysgeusia
- Constipation
- Diarrhea
- Fatigue/asthenia

- Reversible retinal pigment epithelial detachment (RPED or central serous retinopathy [CSR])
- Nausea

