## 8.3 Palbociclib

### 8.3.1 Most common anticipated toxicities (refer to package insert for further details)

- Neutropenia
- Leukopenia
- Anemia
- Thrombocytopenia
- Fatigue
- Nausea

The primary anticipated toxicity of palbociclib is neutropenia. In the phase I trials of palbociclib alone in patients with advanced cancers, neutropenia was the only dose-limiting toxicity (DLT). Grade 3 neutropenia during cycle 1 was observed in 3/22 patients receiving palbociclib 125 mg PO daily, with no grade 4 neutropenic events observed. Based on this result, 125 mg PO daily became the recommended phase II dose (RP2D). Other hematologic AEs of grade 3 or greater during cycle 1 were anemia and leukopenia, occurring in 1 and 4 of 41 patients, respectively. The most common non-hematologic AEs of grade 3 or greater during cycle 1 were fatigue, nausea, and abdominal pain (each occurring in 2 of 41 patients). Of note, there were no complicated hematologic AEs documented, and all hematological AEs resolved during the off drug period of a 3 week on/1 week off schedule, and were non-cumulative.

In a phase II trial of palbociclib alone for advanced breast cancer, the only toxicities grade  $\geq 3$  observed were transient neutropenia (50%) and thrombocytopenia (21%). In a phase II trial of palbociclib plus letrozole for first-line therapy of ER+ MBC, the most common AEs reported were neutropenia, leukopenia, and fatigue. The median time to first treatment delay for neutropenia was 58 days, and the median duration of treatment delay until recovery was 5 days (range 1-16 days). In general, hematological abnormalities were adequately managed with standard supportive care, were not complicated, and resolved during the drug hold with no cumulative toxicity noted. In the phase I dose-escalation trial of palbociclib alone, QT interval changes were also evaluated in detail. While 26 of 41 patients had a maximum increase of <30 msec from baseline QTc, no patients had an on-treatment value exceeding 500 msec.

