### 8.4 Palbociclib and Erdafitinib Dose Modifications and Management of Toxicities

Palbociclib dose level reductions							
Starting dose	First reduction	Second reduction	Third reduction				
125 mg	100 mg	75 mg	Discontinue if no clinical benefit has been seen				
Erdafitinib dose level reductions							
Starting dose	First reduction	Second reduction	Third reduction	Fourth reduction			
8 mg	6 mg	5 mg	4 mg	Discontinue if no clinical benefit has been seen			
6 mg	5 mg	4 mg		Discontinue if no clinical benefit has been seen			
5 mg	4 mg	Discontinue if no clinical benefit has been seen					
Investigations – Hematology (for palbociclib only)							
ANC decreased (Neutropenia)							
Grade 1 / 2	Maintain dose level of palbociclib.						
Grade 3	Omit dose of palbociclib until ANC $\geq$ 1000/mm  , then 
 
- If resolved in <math>\leq</math> 7 days, then maintain dose level of palbociclib.
 
- If resolved in <math>></math> 7 days, then <math>\downarrow</math> 1 dose level of palbociclib.
 
						
Grade 4	Omit dose of palbociclib until ANC $\geq$ 1000/mm  , then $\downarrow$ 1 dose level of palbociclib. Erdafitinib should be omitted as well if the treating physician considers that the safety of the patient is compromised.						
Anemia							
Grade 1 / 2	Maintain dose level of palbociclib.						
Grade 3	Omit dose of palbociclib until resolved to CTCAE Grade $\leq$ 2, then maintain dose level of palbociclib						
Grade 4	Discontinue palbociclib.						
Febrile neutropenia							
Grade 3	Omit dose of palbociclib, then						

	
 
- If resolved by <math>\leq</math> 7 days, then, <math>\downarrow</math> 1 dose level of palbociclib.
 
- If not resolved within 7 days discontinue palbociclib.
 

Grade 4	Discontinue palbociclib. Erdafitinib should be omitted as well if the treating physician considers that the safety of the patient is compromised.
Platelet count decreased (Thrombocytopenia)	
Grade 1 / 2	Maintain dose level of palbociclib.

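### Section 8.4 gives no erdafitinib action for diarrhea at any grade, and its first Grade 2 row conflicts with the dose reduction required by 7.5 after 14 days

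*Combined protocol and SAP*

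**What the plan says.** **The diarrhea rows.** In 8.4, under GI disorders, the block is headed "Diarrhea (for palbociclib only"). Grades 1 to 4 give anti-diarrheal treatment and palbociclib actions only. For a first Grade 2 episode the action is "Omit dose of palbociclib until resolved to CTCAE Grade ≤ 1, then maintain dose level of palbociclib", with no limit on duration. A second Grade 2 episode lowers palbociclib one level, a first Grade 3 does the same, and a second Grade 3 or any Grade 4 stops palbociclib.

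**The toxicity lists.** The erdafitinib list in 8.1.1 includes the run "Constipation - Diarrhea - Fatigue/asthenia". The palbociclib list in 8.3.1 ends "Thrombocytopenia - Fatigue - Nausea" and does not name diarrhea. Each refers to an outside document for detail.

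**The residual rows.** The Other AEs rows at the end of 8.4 cover both drugs: maintain at Grade 1 or 2, stop both at Grade 4, and at Grade 3 "Omit dose of palbociclib and erdafitinib until resolved to CTCAE Grade" 1 or lower, then reduce. Nothing says whether they apply to a drug left out of a named block.

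**The mandatory reductions.** Section 7.5 requires a reduction for Grade 3 or 4 toxicities and for Grade ≥ "2 GI toxicity lasting more than 14 days despite medical treatment". Section 17.2.1 repeats both, with the GI limit given as 2 weeks. Neither names the drug to be reduced.

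**The concern.** Erdafitinib is the investigational drug and the only one whose dose differs between cohorts. Its own list includes diarrhea, yet the rows a site would turn to say nothing about it. A site that follows them literally could reduce or stop palbociclib for Grade 3 or 4 diarrhea and leave erdafitinib unchanged. After a Grade 4 event, 8.5 allows fulvestrant plus erdafitinib to continue once palbociclib has been stopped. A site that applies the Other AEs rows would hold, reduce or stop erdafitinib for the same event. What is at stake is patient safety and consistent management across sites.

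The second issue is a direct conflict. For prolonged Grade 2 diarrhea, following the table means breaking a rule that 7.5 and 17.2.1 state as mandatory.

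**Working it through.** The plan gives no figure to reproduce. The check sets the rules side by side.

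**1. Does the block cover erdafitinib?** Grades naming an erdafitinib action: diarrhea 0 of 4, constipation 4 of 4, mucositis 4 of 4.

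**2. Is single-drug assignment unusual?** Seven non-hematologic blocks in 8.4 belong to one drug: phosphorus, ocular, constipation, diarrhea, skin, nail and fatigue. Six go to erdafitinib, and 8.1.1 lists all six kinds of toxicity. The seventh, diarrhea, goes to palbociclib, whose list omits it. The count leaves out the bleeding block, which sits under hematology; it too is a palbociclib block that 8.3.1 does not name.

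**3. Do the Other AEs rows fill the gap?** The palbociclib-only hematology rows are the best test.
- Grade 4 neutropenia carries its own erdafitinib instruction: omit it if the physician judges safety to be compromised. If the Other AEs rows governed the unnamed drug, erdafitinib would instead be stopped outright, which contradicts that row.
- Grade 3 neutropenia resolving within 7 days keeps palbociclib at the same dose. Under the Other AEs rows, erdafitinib would be held and reduced for the same event, an odd result for an expected palbociclib toxicity.

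The table therefore favors the reading that a block assigned to one drug leaves the other to judgment. It does not say so.

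**4. How far apart are the two readings for erdafitinib?** The levels come from the part of 8.4 headed "Erdafitinib dose level reductions".

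| Diarrhea grade | Named rows only | Other AEs rows applied |
|---|---|---|
| 1 or 2 | no action stated | maintain |
| 3 | no action stated | hold, then one level down |
| 4 | no action stated | discontinue |

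One level down is (8 − 6)/8 = 25.0%, (6 − 5)/6 = 16.7% or (5 − 4)/5 = 20.0%, so about 17% to 25%. A patient already at 4 mg has no lower level and meets the discontinuation rule. At Grade 4 the difference is full dose against none, or 100%.

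**5. What else could act on erdafitinib?**
- 7.4 interrupts the responsible drug, but only for a cycle 1 DLT (for diarrhea, Grade 3 or higher for at least 48 hours despite treatment).
- 7.5 and 17.2.1 require a reduction at Grade 3-4. No drug is named, so the palbociclib reduction or stop may satisfy them.
- 8.3.2 and 8.5 permit action on erdafitinib but do not require it. The toxicity ground for stopping treatment in 7.10 is not graded.
- The erdafitinib precautions in 9.1 point sites to the investigator brochure, which was not available here.

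**6. The prolonged Grade 2 case.** Take a first Grade 2 episode lasting 15 days despite treatment. Since 15 > 14, 7.5 and 17.2.1 require a reduction. Under 8.4, palbociclib resumes unchanged; erdafitinib has no rule, or is maintained if the Other AEs rows apply. Drugs reduced: 0 under either reading. Section 8.3.2 makes the table decide the dose on resumption unless the Protocol Chair agrees otherwise, and no text ranks 7.5 above it.

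**7. Is that mismatch confined to diarrhea?** No. Grade 2 constipation has the same form: "Omit dose of erdafitinib until resolved to CTCAE Grade ≤ 1, then maintain dose level of erdafitinib", whatever the duration. Grade 3 anemia, and Grade 3 neutropenia or fatigue resolving in 7 days or less, also resume at the same dose in 8.4, although 7.5 requires a reduction for Grade 3.

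**The case against.** The strongest defense is that the assignment to palbociclib is deliberate. The neutropenia rows show that such headings leave the other drug to the physician, and fatigue, which is on both lists, is assigned to erdafitinib alone. The toxicity lists are not exhaustive, and the documents do not show which drug causes more diarrhea. This stands in part: a reader might infer that the heading names the wrong drug, and the documents do not establish that. But a deliberate assignment would still leave a listed toxicity of the investigational drug without a stated action.

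A second defense is that 7.5 already compels a reduction at Grade 3-4, and that an erdafitinib reduction is a natural reading because the dose levels differ only in erdafitinib. That also carries weight. A reader might conclude that nothing but discretion stands between the patient and full-dose erdafitinib. That is too strong, because a mandatory rule exists. Its weakness is that it does not say which drug it binds.

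A third is that the 7.5 conflict is not about diarrhea. That is correct, as step 7 shows, and it calls for a general precedence statement rather than a diarrhea edit alone.

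**Conclusion.** The point holds as a gap and an inconsistency, with moderate confidence. The diarrhea block gives no erdafitinib action at any of four grades, and the table's usage suggests that the Other AEs rows do not supply one. Outside a cycle 1 DLT, erdafitinib could stay at full dose through Grade 3-4 diarrhea if the 7.5 reduction is taken to be met by palbociclib and the investigator does not use discretion. For a first Grade 2 episode beyond 14 days, 8.4 reduces no drug although 7.5 and 17.2.1 require a reduction.

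The size in patients is unknown because the documents give no diarrhea rate. A reader might also infer a bias in the MTD or RP2D. The documents show none: the rule of at least 15 tolerant patients out of 20 appears to count the toxicities themselves, whichever drug is then reduced. The conclusion assumes that the brochure and package insert do not already give sites a binding erdafitinib instruction for diarrhea.

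**What to change.** In 8.4, drop the restriction to palbociclib from the diarrhea heading and add these erdafitinib actions, for the clinical team to confirm:

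- Grade 1, and Grade 2 lasting 14 days or less: maintain.
- Grade 2 lasting more than 14 days despite treatment: reduce one level. The team should confirm which drug or drugs the 7.5 reduction applies to.
- Grade 3: hold until Grade 1 or lower, then reduce one level, as in the constipation and Other AEs rows. A patient already at 4 mg follows the existing discontinuation rule.
- Grade 4: discontinue erdafitinib, as in the same rows.

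Add one sentence saying whether 7.5 or the 8.4 table governs where they differ. That also settles the constipation, anemia, neutropenia and fatigue rows.

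The cost is an amendment to one table block plus that sentence. There would be some additional erdafitinib holds, reductions or stops; the number cannot be given without a diarrhea rate. Stopping both oral drugs at Grade 4 means that fulvestrant stops too under 8.5. A stop before week 8 affects who enters the tolerability set, which 17.2.1 limits to patients with at least 8 weeks of erdafitinib, so the team should state how such a patient is counted.

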## 7.10 Discontinuation of Treatment

The reasons for discontinuation or protocol treatment include:

- Evidence of disease progression during treatment at the discretion of the treating investigator
- Non-compliance with the study protocol, including, but not limited to not attending the majority of scheduled visits. The Protocol Chair will determine when non-compliance should lead to removal from study. Note: These patients will still be included in the overall evaluation of safety and response
- Unacceptable major toxicity. Note: These patients will still be included in the overall evaluation of safety and response

- Intercurrent illness or condition that would, in the judgment of the treating investigator, affect assessment of clinical status to a significant degree or require discontinuation of study treatment
- At subject's own request. Note: The reason for discontinuation from the study must be documented. These patients will be included in the overall evaluation of safety and response if any protocol therapy was administered prior to withdrawal
- Study is closed for any reason (e.g. new information shows that the patient's welfare would be at risk if she continued study treatment)
- General or specific changes in the participant's condition render the participant unacceptable for further treatment in the opinion of the treating investigator
- Patients that require a dose delay of > 28 days. If the delay is due to a cause unrelated to study participation, the patient will have the opportunity to continue study if beyond the first 8 weeks of treatment, if clinical benefit is seen, and if deemed eligible to do so by the Protocol Chair of the study
- If the patient requires dose reduction below dose level -1, the patient should be discontinued from the study unless deemed to have clinical benefit that would outweigh the risk. A discussion with the Protocol Chair should be carried out prior to final decision on discontinuation

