7.0-9.0 mg/dL	Omit erdafitinib.  Sevelamer 800 to 1,600 mg 3 times a day with food until phosphate level is <5.5 mg/dL.  Once serum phosphate level returns to <5.5 mg/dL, restart erdafitinib at same dose level.  A dose reduction may be implemented for persistent hyperphosphatemia (≥7 mg/dL) if clinically necessary
>9.0 mg/dL	Omit erdafitinib.  Sevelamer up to 1,600 mg 3 times a day with food  AND  Acetazolamide 250 mg 2 or 3 times a day only until serum phosphate level returns to <5.5 mg/dL.  Once serum phosphate level returns to <5.5 mg/dL, restart treatment at the first reduced dose level.  A second dose reduction may be implemented if needed or clinically indicated for persistent hyperphosphatemia (≥7 mg/dL) at every cycle
>10.0 mg/dL and/or significant alteration in baseline renal function and/or Grade 3 hypocalcemia	Erdafitinib should be discontinued permanently. (In situations where the subject is having clinical benefit and the investigator and the Study Chair agree that re-starting drug is in the best interest of the subject, the drug may be re-introduced at 2 dose levels lower if appropriate. Follow other recommendations described above.)
aNote: Restriction of phosphate intake to 600 – 800 mg/day is recommended to all subjects in the study	
Ocular toxicity (for erdafitinib only)	
Grade 1	Refer to ophthalmologic exam. If this cannot be performed within 7 days, omit erdafitinib until an exam can be performed.  If no evidence of eye toxicity, continue erdafitinib at same dose level.

	
If keratitis or retinal abnormality are detected, omit erdafitinib until signs and symptoms have resolved; follow specific treatment as per ophthalmologist's recommendations.
 
For retinal pathology perform OTC as appropriate and consider referral to a retina specialist for further evaluation.
 
If toxicity is reversible (complete resolution or stabilization and asymptomatic) in 4 weeks according to ophthalmologic exam, resume erdafitinib at the next lower dose level after consultation with Protocol Chair.
 
Monitor for recurrence every 1 to 2 weeks for a month and as clinically appropriate thereafter. If there is no recurrence then re-escalation can be considered in consultation with the medical monitor.
 
If there is no evidence of eye toxicity, continue erdafitinib therapy at the same dose level.

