Grade 2	
Immediately omit erdafitinib and refer to ophthalmologic exam.
 
If keratitis or retinal abnormality are detected, omit erdafitinib until signs and symptoms have resolved; follow specific treatment as per ophthalmologist's recommendations.
 
For retinal pathology perform OTC as appropriate and consider referral to a retina specialist for further evaluation.
 
Monitor for recurrence every 1-2 weeks for a month and as clinically appropriate thereafter.
 
If toxicity is reversible (complete resolution or stabilization and asymptomatic) in 4 weeks according to ophthalmologist exam, resume erdafitinib at the next lower dose level if patient is deriving clinical benefit from treatment, after consultation with Protocol Chair.

Grade 3	
Immediately discontinue erdafitinib, refer to ophthalmologic exam, report as SAE.
 
If keratitis or retinal abnormality are detected, omit Erdafitinib until signs and symptoms have resolved; follow specific treatment as per ophthalmologist's recommendations.
 
For retinal pathology perform OTC as appropriate and consider referral to a retina specialist for further evaluation.
 
If toxicity is reversible (complete resolution or stabilization and asymptomatic) in 4 weeks according to ophthalmologist exam, resume erdafitinib at 2 lower dose levels if patient is deriving clinical benefit from treatment, after consultation with Protocol Chair.
 
Continue to monitor for recurrence of toxicity every 1-2 weeks for a month and as clinically appropriate thereafter, using appropriate investigations. For cases of recurrence, permanently discontinue erdafitinib.

Grade 4	
Immediately discontinue erdafitinib permanently, refer to ophthalmologic exam, report as SAE.
 
Continue to monitor for recurrence of toxicity every 1-2 weeks for a month and as clinically appropriate thereafter, using appropriate investigations.

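### The dose-reduction rules conflict at the bottom of the ladder, and a two-level erdafitinib restart has no dose to go to from 5 mg or 4 mg

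*Combined protocol and SAP*

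**What the plan says.** **Past the lowest dose level.** Four places bear on this.

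- The closing notes of Section 8.4: "Patients who require dose reductions of palbociclib and erdafitinib past the lowest dose level will be discontinued from study drugs treatment". There is no exception for benefit.
- The reduction table that opens Section 8.4 ends the palbociclib row and the 8, 6 and 5 mg erdafitinib rows with "Discontinue if no clinical benefit has been seen". It names no dose for a patient who has benefited.
- Section 7.10: "If the patient requires dose reduction below dose level -1, the patient should be discontinued from the study unless deemed to have clinical benefit". The benefit must outweigh the risk, and the section adds: "A discussion with the Protocol Chair should be carried out prior to final decision on discontinuation".
- Section 8.5 lets a patient who permanently stops either erdafitinib or palbociclib stay on the other drugs under study procedures. All study drugs stop only when both are permanently discontinued.

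**Restarting two levels lower.** In the Section 8.4 ocular table, the Grade 3 row says that if the toxicity reverses within four weeks, sites should "resume erdafitinib at 2 lower dose levels if patient is deriving clinical benefit from treatment", after consulting the Protocol Chair. In the phosphorus table, the row for levels above 10.0 mg/dL makes permanent discontinuation the default. It then adds that, where there is benefit and the investigator and Study Chair agree, "the drug may be re-introduced at 2 dose levels lower if appropriate". Neither row is limited by current dose.

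**The ladder.** The dose table in Section 7.3 lists erdafitinib at 8, 6, 5 and 4 mg for dose levels 3, 2, 1 and -1. Section 7.5 says: "The first cohort of patients (3 patients) will be started at dose level 1". That level is 5 mg.

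**The concern.** These rules tell a site what to do once a patient has run out of reductions, or has had a Grade 3 ocular event or very high phosphate. If one section requires stopping and another permits continuing, two sites can treat the same patient differently and both be following the protocol. If a row points to a dose level that does not exist, a site has to improvise: one step down, a dose off the ladder, or stopping. At stake are patient safety and a uniform record of who was reduced, stopped or continued. The second gap falls on the starting dose of the first cohort.

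**Working it through.** No statistical figure is involved. The check sets the texts side by side and counts steps on the ladder.

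**Step 1. Three patients read against the rules.**

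| Patient | 8.4 closing note | 8.4 reduction table | 7.10 | 8.5 |
|---|---|---|---|---|
| Both drugs past lowest level, benefiting | Stop | Stop not required; no dose given | May continue if benefit outweighs risk, after Chair discussion | All drugs stop if both are permanently discontinued; silent on whether they must be |
| Erdafitinib only past lowest level, benefiting | Stop if the note applies per drug; silent if it needs both | Stop not required; no dose given | As above | If erdafitinib is stopped, the others may continue |
| Erdafitinib only past lowest level, no benefit | As above | Stop erdafitinib | Off the study | The others may continue under study procedures |

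The first line is an outright conflict on any reading: the closing note requires a stop that the table and Section 7.10 do not. The second line depends on how the words joining the two drugs in the closing note are read. The third shows that the object of stopping differs too: the study in 7.10, study drug treatment in the closing note, and the individual drug in the table and in 8.5.

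So there are three wordings of the rule but two opposed answers on whether stopping is mandatory. The table and 7.10 agree in direction and differ in condition.

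A further ambiguity is that Section 7.10 is keyed to dose level -1, at which Section 7.3 sets palbociclib at 125 mg. How it applies to palbociclib below 75 mg, the last step of the palbociclib row, is not stated.

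**Step 2. Steps available on the erdafitinib ladder (8-6-5-4 mg, Sections 7.3 and 8.4).**

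| Current dose | One level lower | Two levels lower |
|---|---|---|
| 8 mg | 6 mg | 5 mg |
| 6 mg | 5 mg | 4 mg |
| 5 mg | 4 mg | none |
| 4 mg | none | none |

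Two of the four levels have no dose two levels lower. The gap also reaches patients who started higher: a 6 mg starter after one single-level reduction (6 to 5), and an 8 mg starter after two (8 to 6 to 5).

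**Step 3. Which row is exposed.** The phosphorus row keeps a usable default at every dose, namely permanent discontinuation; only its optional restart is undefined at 5 and 4 mg, and that restart is qualified as being where appropriate. The Grade 3 ocular row has no such qualifier. For a patient whose toxicity has reversed and who is benefiting, its restart instruction cannot be carried out at 5 or 4 mg.

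**The case against.** The strongest reply is that nobody restarts unsupervised. Section 8.3.2 allows departures from the table criteria by agreement with the Protocol Chair, Section 8.5 sends proposed changes to the Chair in advance, and both restart rows require consultation or agreement. This stands as mitigation: each case should reach a named decision-maker. It does not say which of two opposed rules is the default from which a departure is being sought, and it does not supply the missing level.

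A second reply is that the closing note names both drugs and, read with Section 8.5, concerns only patients who have exhausted both. That reading is reasonable and narrows the conflict. It does not remove it, as the first line of Step 1 shows.

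A reader might also infer several stronger points, which the documents do not support:

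- **That the Grade 3 ocular row contradicts itself by discontinuing and then resuming.** Only the Grade 4 row adds that discontinuation is permanent, and the Grade 3 row goes on to speak of omitting drug until resolution. It reads as a hold with a conditional restart.
- **That the absence of a 4 mg starting row is a separate defect.** There is no lower step to tabulate, and Section 7.10 already speaks to reductions below dose level -1. It is the same conflict counted again.
- **That the quoted incidences show how often these rows will apply.** The 14.4% for central serous retinopathy (Section 8.1.2) is at 8 or 9 mg, with most events Grade 1 or 2. The 65.2% for hyperphosphatemia (Section 8.1.3.2) is any reported event, and the maximum mean phosphate given there is 7.3 mg/dL, at 9 mg. Neither measures the triggers of these rows, and no frequency is given at 5 or 4 mg.
- **That the ambiguity shifts the count of tolerant patients.** Section 17.2.1 requires 8 weeks without the cited toxicities, and Grade 3 or 4 toxicity is among them (Sections 7.5 and 17.2.1). A Grade 3 ocular event already fails, whether erdafitinib is stopped or resumed.

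**Conclusion.** The concern holds in two parts. First, the closing note of Section 8.4 is opposed to the reduction table and Section 7.10 on whether a patient past the lowest dose must stop. With Section 8.5, the texts also leave open what is stopped and whether the note applies to one drug or only to both. Second, the two-level erdafitinib restart is undefined at two of four dose levels, 5 and 4 mg, including the first cohort's starting dose and anyone already reduced to those doses. This bites mainly in the Grade 3 ocular row.

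The conclusion rests on the ladder as printed in Sections 7.3 and 8.4, and on taking a dose level to mean a step on that ladder. The size is one of conduct and safety: sites cannot follow these rules as written. How many patients would be affected cannot be estimated from the documents, and no sample size, power or error rate changes. It should be corrected.

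**What to change.** Reconcile Section 7.10, the reduction table and closing note of Section 8.4, and Section 8.5 to a single rule for a patient past the lowest dose level. State whether it applies to each drug separately or only when both are exhausted, what is stopped (the drug, all study drugs, or study participation), and how it applies to palbociclib. Reconcile the Grade 3 ocular row and the row for phosphorus above 10.0 mg/dL with the ladder, so that each current dose (8, 6, 5 and 4 mg) has a defined outcome. The clinical leads must decide the content of both; this review takes no position on it.

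The cost is wording in Sections 7.10, 8.4 and 8.5, made as a protocol amendment with the IRB approval that Section 15.2 requires. It adds no visits, procedures or patients.
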